5.3 Treatment Assignment Procedures

5.3.1 Randomization Procedures

Once consented and upon entry of demographic data and confirmation of eligibility for this study, the subject will be enrolled. Approximately 50 subjects will be assigned randomly to 1 of 4 treatment arms, in a 3:3:3:1 ratio. The first treatment arm (n=15) will be vaccinated with one dose of 10⁷ CFU BPZE1 using the VaxINator device. The second treatment arm (n=15) will be vaccinated with one dose of 10⁹ CFU BPZE1 using the VaxINator device. The third treatment arm (n=15) will be vaccinated with one dose of placebo via VaxINator device. The fourth treatment arm (n=5) will be vaccinated with one dose of 10⁹ CFU BPZE1 using a needleless tuberculin syringe.

Enrollment of subjects will be done online using the enrollment module of AdvantageEDCSM. The randomization code will be prepared by statisticians at the DCC and included in the enrollment module for this study. AdvantageEDCSM will assign each subject to a treatment arm after the demographic and eligibility data have been entered into the system. A designated individual at the participating VTEU site will be provided with a code list for emergency unblinding purposes, which will be kept in a secure location.

Instructions for use of the enrollment module are included in the AdvantageEDCSM User's Guide. Manual back-up procedures and instructions are provided for use in the event that the

participating VTEU site temporarily loses access to the Internet or the online enrollment system is unavailable.

5.3.2 Masking Procedures

This is a partially-blind clinical study as the method of immunization (i.e., VaxINator vs. needleless syringe) will be known. After reconstitution and transfer to a 1-mL syringe, the 10^7 CFU dose investigational vaccine and the placebo are transparent and indistinguishable while the 10^9 CFU dose can be discriminated from the placebo and the 10^7 CFU dose due to its opaque appearance. Therefore, syringes will be wrapped with a colored sleeve to avoid potential unblinding of study personnel or the subject. Investigators, the subject, and study personnel will remain blinded to allocation of BPZE1 or placebo.

The randomization scheme will be generated by the DCC and provided to unblinded study personnel (i.e., research pharmacists performing study vaccination preparations and unblinded study vaccine administrators) at the participating VTEU site.

The unblinded study vaccine administrator is a study personnel member credentialed to administer vaccines and may also participate in dose preparation, but will not be involved in study-related assessments or have subject contact for data collection following study vaccine administration.

Laboratory personnel performing immunogenicity assays will be blinded to study assignment. Upon request by the participating VTEU site, and at the discretion of DMID, unmasking may occur after all data have been locked at Day 181, analyzed, interpreted, and the final CSR has been completed.

The Safety Monitoring Committee (SMC) may receive data in aggregate and presented by treatment arm. The SMC may also be provided with expected and observed rates of the expected AEs in an unblinded fashion and may request the treatment arm be unblinded for an individual subject if required for safety assessment. The SMC will review grouped and unblinded data in the closed session only.

5.3.3 Reasons for Withdrawal

Subjects may voluntarily withdraw their consent for study participation at any time and for any reason, without penalty or loss of benefits to which they are otherwise entitled.

An investigator may also withdraw a subject from receiving the study product for any reason. Follow-up safety evaluations will be conducted, if the subject agrees. If a subject withdraws or is withdrawn prior to completion of the study, the reason for this decision must be recorded in the case report forms (CRFs).

The reasons, might include, but are not limited to the following:

1. Subject no longer meets eligibility criteria
2. Subject meets individual halting criteria
3. Subject becomes noncompliant
4. Medical disease or condition, or new clinical finding(s) for which continued participation, in the opinion of the investigator might compromise the safety of the subject, interfere with the subject's successful completion of this study, or interfere with the evaluation of responses
5. Subject lost to follow-up
6. Subject becomes pregnant, if applicable
7. Determined by a physician's discretion to require additional therapy not indicated in the protocol to ensure subject's health and well-being (or treatment failure, if applicable)

The investigator should be explicit regarding study follow-up (e.g. safety follow-up) that might be performed. If the subject consents, every attempt will be made to follow all AEs through resolution. The procedures that collect safety data for the purposes of research must be inclusive in the original informed consent or the investigator may seek subsequent informed consent using an IRB/IEC-approved consent form with the revised procedures.

The investigator will inform the subject that already collected data will be retained and analyzed even if the subject withdraws from this study.

5.3.4 Handling of Withdrawals

The primary reason for withdrawal from this study will be recorded on the appropriate data collection form. Subjects will be encouraged to complete the Early Termination Visit. The Early Termination Visit procedures are listed in [Section 7.5](#).

Although subjects are free to withdraw at any time or may be withdrawn by the site principal investigator or appropriate sub-investigator at any time, subjects will be encouraged to remain in this study for follow-up safety assessments (may be conducted by phone rather than in person) continuing through approximately 6 months after study vaccination. These subjects will also be

encouraged to provide a venous blood sample for serological assessment at approximately 28 days after study vaccination. See the protocol-specific Manual of Procedures (MOP) for alternate follow-up requirements.

Every attempt will be made to follow all adverse events, including systemic reactions, unsolicited non-serious adverse events, and serious adverse events ongoing at the time of early withdrawal through resolution.

For subjects who fail to appear for a follow-up safety assessment, extensive effort (e.g., three documented contact attempts via phone calls, e-mails, etc., made on separate occasions and followed by a certified letter) will be made to locate them. Any questions to determine their health status will be made by phone or visit by the subject. These efforts will be documented in the subject's study records.

5.3.5 Subject Replacement

Subjects who withdraw, are withdrawn/terminated from this study, or are lost to follow-up after signing the informed consent form and randomization but before receipt of study vaccine may be replaced. Subjects who are vaccinated, but do not complete the Day 15 visit, will be replaced. Subjects who are vaccinated and subsequently, after the Day 15 visit, withdraw, are withdrawn or terminated from this study, or are lost to follow-up will not be replaced. Subjects who were previously screened and found to be ineligible due to initial serum concentrations of PRN IgG \geq 20 IU/ml in protocol version 3.0 may be rescreened per the revised exclusion criterion of protocol version 4.0.

5.3.6 Termination of Study

Although the sponsor has every intention of completing this study, it reserves the right to terminate the study at any time for clinical or administrative reasons. Reasons for termination include, but are not limited to, study closure due to SMC recommendation and at the discretion of DMID.

If the study is prematurely terminated by the sponsor, any regulatory authority, or the investigator for any reason, the investigator will promptly inform the study subjects and assure appropriate therapy or follow-up for the subjects, as necessary. The investigator will provide a detailed written explanation of the termination to the IRB/IEC.

6 STUDY INTERVENTION/INVESTIGATIONAL PRODUCT

6.1 Study Product Description

BPZE1 investigational vaccine

The investigational BPZE1 lyophilized vaccine is for nasal administration and contains

| | | |
|------------|------------|------------|
| [REDACTED] | [REDACTED] | [REDACTED] |
| [REDACTED] | [REDACTED] | [REDACTED] |
| [REDACTED] | [REDACTED] | [REDACTED] |
| [REDACTED] | [REDACTED] | [REDACTED] |
| [REDACTED] | [REDACTED] | [REDACTED] |
| [REDACTED] | [REDACTED] | [REDACTED] |
| [REDACTED] | [REDACTED] | [REDACTED] |
| [REDACTED] | [REDACTED] | [REDACTED] |
| [REDACTED] | [REDACTED] | [REDACTED] |
| [REDACTED] | [REDACTED] | [REDACTED] |
| [REDACTED] | [REDACTED] | [REDACTED] |
| [REDACTED] | [REDACTED] | [REDACTED] |
| [REDACTED] | [REDACTED] | [REDACTED] |
| [REDACTED] | [REDACTED] | [REDACTED] |
| [REDACTED] | [REDACTED] | [REDACTED] |

Two BPZE1 investigational vaccines with different strengths (expressed as colony forming units (CFU) per mL or per dose), composed of BPZE1 at 10^7 and 10^9 CFU/dose, are to be evaluated. Each individual investigational vaccine vial, after reconstitution, contains 1 mL of BPZE1 suspension.

Placebo

The placebo consists of the same constituents in the same quantities as the BPZE1 investigational vaccines, absent the attenuated *B. pertussis* cells.

VaxINator atomization device

BPZE1 investigational vaccine or placebo will be administered nasally via the VaxINator atomization device attached to a 1 mL syringe. The VaxINator is manufactured by Teleflex Medical. Teleflex has a Master File (MF #16712) for the VaxINator. The VaxINator is a conical shape plastic component that Luer-locks onto a standard syringe. The VaxINator atomizes the liquid vaccine as it exits the syringe. The conical shape forms a plug in the nostril and high applied-pressure atomizes the liquid into a fine mist.

6.1.1 Acquisition

6.1.1.1 BPZE1 vaccine and Placebo

Individual boxes of packaged and labeled investigational vaccine/placebo contain investigational vaccine/placebo. The boxes shall be shipped from [REDACTED] for distribution to the clinical site. All boxes of investigational vaccine/placebo will be shipped at below -20 C with temperature logging devices and should be stored at -10°C or below after arrival to the site.

6.1.1.2 Additional Components

VaxINator kits are supplied in individual sterile pouches containing a VaxINator atomization device, a 1-mL single-use syringe, and other accessories not utilized in the current protocol that will be discarded. VaxINator kits will be shipped from [REDACTED] for distribution to the clinical site.

[figure not shown]
The following additional components will be sourced by [REDACTED] for distribution to the clinical site:

- 1) 18G x 1 ½", sterile needles in a box containing 100 units in total
- 2) 1-mL, sterile, tuberculin syringes in a box containing 100 units in total

All boxes of components and VaxINators (excluding investigational vaccine or placebo) should be stored at ambient temperature.

Upon request by DMID, BPZE1 vaccine, Placebo and VaxINator atomization device and additional components will be transferred to the following address:

The Investigational Drug Service Pharmacy will provide sterile Water for Injection (SWFI) needed for study drug dilution.

BPZE1 vaccine, Placebo and VaxINator atomization device and additional components will be provided through the DMID CMS to the participating sites prior to the start of this trial upon request and with prior approval from DMID.

6.1.2 Formulation, Packaging, and Labeling

BPZE1 vaccine and Placebo

The primary packaging is a sterile glass 2R DIN vial with a chlorobutyl lyophilization stopper. The vial closure system is a combination of the stopper and the aluminum cap. The vials are crimped directly after the lyophilization process using the automated Fill & Finish unit that filled the vials with 1.0 mL suspension.

One vial for administration will be prepared for each subject in the clinical trial, typically packaged in a box of 10 vials (sufficient for 10 subjects). The box complies with the safety regulations for GMO storage and shipment. The vials and the boxes will be labeled with the required information applicable to investigational vaccine or placebo product used in clinical trials. The boxes either contain the vaccine or the placebo, typically as 10 vials per box.

A single VaxINator kit (sterile pouch containing a VaxINator atomization device, a 1-mL single-use syringe, and other accessories not used in this protocol to be discarded) is provided for each subject in groups 1, 2, and 3. The boxes will be labeled with the required information applicable to a medical device accessory, for clinical trial investigational use only.

The 18G x 1 ½", and tuberculin syringes to reconstitute the investigational vaccine or placebo vials will be stored separately from the investigational vaccine pouches at ambient temperature. For each individual subject, the participating site research pharmacist will fill a 1-mL tuberculin syringe with SWFI for reconstitution.

The placebo consists of the same constituents in the same quantities as the BPZE1 investigational vaccines, absent the attenuated *B. pertussis* cells. After reconstitution and transfer to a 1-mL syringe, the 10^9 CFU dose can be discriminated from the placebo and the 10^7 CFU dose due to the opaque appearance of the 10^9 CFU dose BPZE1 investigational vaccine, while the placebo and the 10^7 CFU dose investigational vaccine are transparent. The 10^7 CFU dose investigational vaccine and the placebo are indistinguishable after reconstitution.

The study product will be labeled according to manufacturer specifications and include the statement “Caution: New Drug – Limited by Federal Law to Investigational Use.”

Further details are included in the *Bordetella pertussis* vaccine (BPZE1) IB, as well as in the protocol-specific MOP.

6.1.3 Product Storage and Stability

BPZE1 vaccine and Placebo

Both BPZE1 and placebo product will be stored at -10°C or less until ready for use in order to maintain viability of BPZE1 prior to reconstitution with SWFI. The exposure of reconstituted BPZE1 to room temperature prior to vaccination should not exceed 60 minutes. A detailed description regarding the storage, reconstitution and handling the investigational vaccines is given in the Manual of Procedures (MOP).

VaxINator devices are stored at ambient temperature.

Additional details of product storage and stability can be found in the MOP.

6.2 Dosage, Preparation and Administration of Study Intervention/Investigational Product

See the protocol-specific MOP for detailed information on the preparation, labeling, storage, and administration of study vaccine for each treatment arm. Study vaccine preparation will be performed by the participating site research pharmacist.

For those randomized to the VaxINator groups, a full-dose (i.e., 800 μL containing 10^7 or 10^9 CFU) will be drawn into one 1 mL syringe from the vial, the VaxINator tip connected, and 400 μL volume will be administered to each nostril. The VaxINator provides a uniform, controlled delivery, which allows the clinician to accurately deliver 400 μL of vaccine to the initial nostril and then administer the remaining 400 μL to the opposite nostril.

For those randomized to administration via needleless tuberculin syringe, the same procedures will be followed, deleting the connection of a VaxINator tip.

The dose of BPZE1 active ingredient or placebo will be administered to the volunteer within 60 minutes of reconstitution.

For the 10^9 CFU vaccine dose, one mL of SWFI is used to reconstitute the 1 mL vial of lyophilized BPZE1, but only 800 μ L of vaccine are used for administration into both nostrils. The SWFI will be drawn into 1 mL syringes, the 1 mL SWFI will be injected into the lyophilized BPZE1 vial for reconstitution, 900 μ L vaccine dose will be withdrawn into a separate 1 mL syringe, the plunger will be expelled to the 0.8-mL mark, the VaxINator shall be attached to the syringe, and 400 μ L volume will be administered to each nostril. The VaxINator provides a uniform, controlled delivery, which allows the vaccinator to accurately deliver 400 μ L of vaccine to the initial nostril and then administer the remaining 400 μ L to the opposite nostril.

For the 10^7 CFU vaccine dose, three 1 mL SWFI-filled syringes and two placebo cryovials are used to reconstitute and dilute the 1 mL vial of lyophilized 10^9 BPZE1. The SWFI will be injected into each of the placebo cryovials and the 1 mL vial of lyophilized BPZE1. Two serial dilutions (10-fold and 100-fold) of the reconstituted 10^9 CFU vaccine will be done to prepare a 10^7 CFU vaccine dose. A 900 μ L vaccine dose will be withdrawn into a separate 1 mL syringe, the plunger will be expelled to the 0.8-mL mark, the VaxINator shall be attached to the syringe, and 400 μ L volume will be administered to each nostril. The VaxINator provides a uniform, controlled delivery, which allows the vaccinator to accurately deliver 400 μ L of vaccine to the initial nostril and then administer the remaining 400 μ L to the opposite nostril. To avoid accidental exposure to the environment and to study staff, actions should be taken to minimize generation of aerosols, since the bacteria are strictly respiratory tract organisms. Staff members should wear eye-protective glasses during the vaccination. Persons handling BPZE1 should wear gloves and must practice standard hand hygiene before touching their skin or eyes.

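### The protocol gives conflicting accounts of how the 10^7 CFU dose is supplied and prepared, and one reading of its dilution sentence misses the target named in that sentence

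*Protocol*

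**What the plan says.** **A strength of its own, one vial per subject.** Protocol Section 6.1 speaks of two vaccines of different strength, "composed of BPZE1 at 10^7 and 10^9 CFU/dose, are to be evaluated", and adds: "Each individual investigational vaccine vial, after reconstitution, contains 1 mL of BPZE1 suspension". Section 6.1.2 says "One vial for administration will be prepared for each subject in the clinical trial", treats a box of ten vials as enough for ten subjects, and has the pharmacist fill one 1 mL syringe of sterile water (SWFI) for each subject. It describes the 10^7 product as reconstituted and does not mention dilution: "The 10^7 CFU dose investigational vaccine and the placebo are indistinguishable after reconstitution". The opening of Section 6.2 covers both dose levels together. A full dose is 800 µL holding 10^7 or 10^9 CFU, which "will be drawn into one 1 mL syringe from the vial, the VaxINator tip connected".

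**Prepared from the 10^9 vial.** Further on, Section 6.2 says that for the 10^7 dose "three 1 mL SWFI-filled syringes and two placebo cryovials are used to reconstitute and dilute the 1 mL vial of lyophilized 10^9 BPZE1", and then: "Two serial dilutions (10-fold and 100-fold) of the reconstituted 10^9 CFU vaccine will be done to prepare a 10^7 CFU vaccine dose". It gives no transfer volumes.

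**Basis of strength.** Section 6.1 allows strength per mL or per dose. Section 6.2 ties the stated CFU to 800 µL in its opening, but later labels the source as a 1 mL vial of 10^9. For the 10^9 dose, "one mL of SWFI is used to reconstitute the 1 mL vial of lyophilized BPZE1", of which 800 µL is given.

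**What is constant.** Protocol Sections 4 and 5.3.1 and the SAP (Sections 4.1 and 4.4.3, and the table shells) name the arm 10^7 CFU throughout. Section 6.2 begins by referring the reader to the Manual of Procedures (MOP) for detailed preparation in each arm.

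**The concern.** Section 11.4 says the results will inform the dose for Phase 2b, and 10^7 against 10^9 CFU is the dose contrast in the trial. The text defining what one of those two arms receives should therefore have one meaning. As written, a reader cannot tell from the protocol whether the 10^7 product arrives as its own strength or is made at the site. If it is made at the site, the dilution sentence can be read in two ways that differ tenfold.

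The supply accounts also feed product accountability (Section 6.4). A monitor checking placebo vials used against the protocol would expect different numbers depending on which section is followed. Appearance offers no check, because the 10^7 preparation and the placebo are both transparent (Sections 5.3.2 and 6.1.2).

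**Working it through.** **1. The plan's own figure.** Dose = starting CFU / total dilution. With 10-fold and 100-fold as cumulative levels, the total is 100-fold, and 10^9 / 100 = 10^7 CFU. This reproduces the dose named in the sentence.

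**2. The other reading.** With a 10-fold step followed by a 100-fold step, the total is 10 × 100 = 1000-fold, and 10^9 / 1000 = 10^6 CFU. That is one log10 below the named dose.

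**3. Basis of strength.** CFU given = (CFU per mL of reconstituted vial) × 0.8 mL / dilution. If 10^9 CFU is held in 0.8 mL, the 1 mL vial holds 10^9 / 0.8 = 1.25 × 10^9.

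| What 10^9 refers to | Undiluted | 100-fold total | 1000-fold total |
|---|---|---|---|
| the 0.8 mL given | 1.0 × 10^9 | 1.0 × 10^7 | 1.0 × 10^6 |
| the full 1 mL vial | 8.0 × 10^8 | 8.0 × 10^6 | 8.0 × 10^5 |

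The basis alone is a factor of 1.25. It moves the 10^9 and 10^7 arms together, so the 100-to-1 contrast is unchanged (10^9 : 10^7, or 8 × 10^8 : 8 × 10^6).

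**4. Supplies at the planned sizes.** The arms have 15 (10^7), 15 (10^9), 15 (placebo) and 5 (10^9 by syringe) subjects. I assume one placebo vial and one water syringe per placebo recipient, as Section 6.1.2 implies, and no wastage or replacements.

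| | Separate strength (6.1, 6.1.2, opening of 6.2) | On-site dilution (later in 6.2) |
|---|---|---|
| Placebo vials | 15 | 15 + 2 × 15 = 45 |
| BPZE1 vials | 15 of 10^7 and 20 of 10^9 | 35 of 10^9 |
| Water syringes | 50 | 35 + 3 × 15 = 80 |

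The number of BPZE1 vials is the same (35), but their strength, the placebo use (threefold) and the water syringes are not.

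**5. Transfer volumes.** Into 1 mL of diluent, an F-fold step needs 1000 / (F − 1) µL: 1000 / 9 = 111 µL for 10-fold and 1000 / 99 = 10.1 µL for 100-fold. The protocol states neither volume.

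**The case against.** The strongest reply is that the dilution sentence carries its own answer. It names a 10^7 target and starts from 10^9, and only a 100-fold total connects the two. The listed materials point the same way: two 1 mL placebo vials and 1 mL syringes suit two steps of roughly 0.1 mL more readily than a 10 µL transfer. This stands. The 1000-fold reading is not an equally open option. What remains is that an instruction which must be checked against its own target to be understood is poorly worded for a preparation step.

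Second, the working detail is in the MOP, which is not among the documents and may be entirely clear. This also stands, and it is why missing transfer volumes alone are no fault in the protocol. It does not remove a conflict between sections of the protocol itself.

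Third, Section 6.1 never says outright that a 10^7 vial is manufactured, and part of its formulation text is redacted. The vial prepared for administration in Section 6.1.2 could be the final diluted one. This weakens Section 6.1 as evidence. However, Section 6.1.2 still gives one water syringe per subject against three, and says nothing of placebo vials used as diluent. The opening of Section 6.2 still draws either dose directly from the vial.

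A reader might also infer that colonisation is steep in dose here, so that a tenfold slip would be decisive. The documents do not support that. Phase 1a (Sections 2.1 and 2.1.1) had 1 of 12 colonised at 10^5 and 5 of 12 at 10^7. With 6 colonised among 24, the two-sided Fisher p is 2 × (C(12,0)·C(12,6) + C(12,1)·C(12,5)) / C(24,6) = 2 × (924 + 9504) / 134596 = 0.155. Phase 1b, at 400 µL per nostril as here, found colonisation unrelated to dose from 10^7 upward (Section 2.1.2). Neither study tested 10^6.

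**Conclusion.** The protocol is wrong as written, in a limited sense. Its account of how the 10^7 dose is supplied and prepared contradicts itself between Sections 6.1, 6.1.2 and the opening of 6.2 on one side, and the later 10^7 instructions in 6.2 on the other. The dilution sentence does not say whether its factors are cumulative or successive. The successive reading gives 10^6 CFU and disagrees with the stated 10^7. At the planned sizes, expected placebo use is 15 or about 45 vials. The basis of strength adds a smaller inconsistency of 1.25-fold, common to both dose levels.

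A reader might infer that the dose given in this arm is not fixed, or that subjects will receive 10^6 CFU. The documents do not support either. The intended dose is 10^7 CFU wherever the arm is named, the dilution sentence itself ends at 10^7, and the operative steps are in a Manual not available here. Nor does the identical appearance of the 10^7 dose and placebo show that an error is likely; it means only that appearance would not reveal one.

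The conclusion rests on the protocol text alone. No view is taken on which preparation or dose is right.

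**What to change.** The sponsor should reconcile Sections 6.1, 6.1.2 and 6.2 with each other and with the MOP:

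- State whether the 10^7 product is supplied as its own strength or prepared from the 10^9 vial, and use that account in all three sections.
- If it is prepared, state whether the two dilution factors are cumulative or successive, so that the sentence agrees with its own target.
- Make the per-subject counts of BPZE1 vials, placebo vials and water syringes match the scheme that holds.
- Express strength on one basis (per mL, per vial or per 800 µL) throughout.

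Step-by-step volumes may stay in the MOP if it agrees with the corrected text. No measured CFU count of prepared doses is requested, since that would be an added procedure. The cost is protocol wording and a check against the MOP, with no extra subjects, visits or assays.
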